## WHF

Time to worsening heart failure through Day 5 will be analyzed using Gehan's generalized Wilcoxon test at an initial significance level of  $(1/5)\alpha$  within a sequentially rejective multiple testing procedure described in detail in [Section 10.5.1](#).

Number and percentage of patients who experienced WHF based on the number of patients in the population as denominator will be provided by treatment group. The hazard ratio (relative risk) and its associated two-sided 95% confidence interval will be estimated based on a Cox proportional hazards model with treatment assignment as a factor.

Kaplan-Meier curves will be presented graphically by treatment group and Kaplan-Meier estimates for selected time points with 95% confidence intervals will be tabulated.

The SAS procedures PHREG and LIFETEST will be used to conduct the analyses [*SAS/STAT User's Guide, version 9.3*].

### 10.4.3 Handling of missing values/censoring/discontinuations

A patient without an event will be censored for CV death at the earlier of:

- Date of death for non-CV related causes
- The last date at which the vital status was known
- Day 180

A patient without a WHF event will be censored at the earlier of the last contact date, withdrawal of consent date or 120 hours after randomization.

### 10.4.4 Supportive analyses

In addition to the primary analyses, the primary efficacy variable, CV death and WHF will also be analyzed using the same primary analysis model on the Per Protocol set as supportive information. Subgroup (age [65 and 75 cut off], gender, race, region, PEF/REF, naïve vs prior history of HF) analyses will be analyzed for both primary endpoints for FAS.

The survival function for each treatment arm will be estimated by the Kaplan-Meier-technique and the Kaplan-Meier curves will be presented for both FAS and PP. The proportion of patients with a primary endpoint will be estimated from the Kaplan-Meier curve for each treatment.

Sensitivity analyses will also be performed using a modified definition of WHF, for example where both signs and symptoms are present.

## 10.5 Analysis of secondary variables

### 10.5.1 Efficacy variables

There are three key secondary efficacy variables defined in this study:

[figure not shown]
- Time to all-cause death through Day 180
- Length of total hospital stay (LOS) during the index AHF hospitalization
- Time to first occurrence of the composite endpoint of CV death or rehospitalization due to heart failure (HF)/renal failure (RF) through Day 180

The key secondary efficacy endpoint of all-cause mortality through Day 180 will not be formally incorporated in a multiple testing procedure. It will be tested with a full  $\alpha$  (two-sided) by itself if one or both of the primary endpoints, CV death or WHF is statistically significant.

The other two key secondary variables will be tested using a sequentially rejective multiple testing procedure in testing LOS and composite of CV death or rehospitalization due to HF/RF (CVDR) in controlling overall  $\alpha$  (Bretz, et al 2009). Figure 10-1 illustrates this multiple testing procedure for two primary and two key secondary variables with strong control of overall  $\alpha$  level of 5%. Note: although CV death will be tested initially at 0.02 (one-sided) significance level and WHF at 0.005 (one-sided) significance level, the final significance level for CV death and WHF will be updated according to the graphical testing strategy incorporating two secondary variables, LOS and CVDR, as depicted in Figure 10-1.

**Figure 10-1**      **Sequentially rejective multiple testing procedure for two key secondary efficacy variables**

Where CVD is CV death, WHF is worsening heart failure, LOS is length of hospital stay, and CVDR is CV death or rehospitalization due to heart failure or renal failure.

The time-to-event (from randomization to the event) analysis similar to the primary analysis of CV death will be used for the analyses of all-cause death at Day 180, and composite of CV death or rehospitalization due to HF or renal failure at Day 180. Patients without an event will be censored at the earlier of the last contact date or Day 180.

Length of stay will be defined as the index hospitalization discharge date and time minus the randomization date and time. Patients still in the hospital at Day 60 will be censored at Day 60. Patients who die during the initial hospitalization will be assigned the maximum length of stay (including those censored at Day 60) + 1 day. Treatment groups will be compared using a Wilcoxon rank sum test.

Other secondary efficacy variables will comprise:

- Length of ICU and/or CCU stay for the index AHF hospitalization
- Change from baseline in congestive signs and symptoms of HF through Day 5
- Change from baseline in selected biomarkers from baseline through Day 14 in a subset of randomized patients

The length of ICU and/or CCU stay for the index AHF hospitalization will be analyzed similarly to the length of hospital stay. Change from baseline in congestive signs and symptoms of HF through Day 5 ([Section 16 Appendix 3](#)) will be analyzed by displaying the percentage of patients (with asymptotic 95% CIs) by treatment and time points for each of the signs and symptoms variables. A time-to-event (response defined as  $\geq 1$  point improvement from baseline) analysis will be applied to provide treatment comparisons. Hazard ratios (serelaxin/placebo) of being a responder for each of the signs and symptoms variables will be estimated using a Cox regression model stratified by region with treatment as a factor. Detailed biomarker analyses will be included in the biomarker substudy protocol.

### 10.5.2 Safety variables

The incidence of AEs recorded through Day 5 and the incidence of SAEs recorded through Day 14 will be presented for the Safety Set. Incident AEs will be considered those AEs with an onset date and time *after* the initiation of study drug. Adverse events with an onset between informed consent and study drug initiation will be listed separately. Adverse events will be coded using the most current version of MedDRA. All reported AEs will be summarized by system organ class (SOC) and preferred term by treatment groups. Serious AEs (SAEs) will be summarized similarly.

In addition, AEs will be summarized by time period of onset: from study drug initiation to Day 5, or from Day 6 to Day 14. Additionally, a summary of AEs by preferred term and severity, using the worst reported severity grade for each event for the subject, will be provided. For analysis purposes, all AEs defined as “definite”, “probable” or “possible” will be considered as related. If the relationship to study drug is unknown or missing, the AE will be considered to be drug-related. All study-drug-related AEs, AEs with an outcome of death, AEs leading to discontinuation of treatment, and study-drug-related SAEs, SAEs with an outcome of death, and SAEs leading to study drug discontinuation will be summarized by percentages and

frequencies. Percentages will be based on the number of patients in the Safety Set. For the analysis by time period of onset, the percentages will be based on the number of patients in the Safety Set with the corresponding AE form completed.

Laboratory data will be summarized by presenting shift tables using extended normal ranges (baseline to most extreme post-baseline value), summary statistics of raw data and change from baseline (means, medians, standard deviations, 1st and 3rd quartiles, Q1 and Q3) and by flagging of notable values in data listings.

For vital signs, descriptive statistics will be provided for values and change from baseline at each assessment time point for pulse, respiratory rate, body temperature, and weight. Treatment groups will be compared for changes from baseline using t-tests.

The number and proportion of patients who experience a confirmed blood pressure decrease event during study drug administration will be provided. Among patients who experience a confirmed blood pressure decrease event, the events will be further characterized. Summaries will be provided separately for those confirmed events that resulted in study drug dose reduction, and those that resulted in study drug discontinuation. The possible interaction between the effect of serelaxin and the effect of IV nitrate administration within the first 48 hours will be examined.

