f At screening, a locally-analyzed sample will be obtained for female patients of child-bearing potential to qualify the patient for study entry.

g Chest X-ray may be interpreted by the study physicians or physicians attending to the patient. Interpretation and the person interpreting the radiograph must be recorded in the source documentation. A radiologist’s interpretation is not necessary for the purposes of the study.

h A complete physical will be performed at screening; an abbreviated physical examination will be performed at all other specified timepoints. Following randomization, all physical examinations should be performed daily at approximately the same time of day. Daily vital signs measurements may be made and recorded by trained study personnel as well as trained healthcare personnel as part of their routine clinical duties. The first recorded measurement per day will be used as the daily measurement for that day. Refer to [Section 6.5.1](#).

 BP and HR measurements are to be performed at 30 & 60 minutes and then every hour for the first 6 hours of study drug infusion, and then every 3 hours during study drug infusion, including night time hours. Post-infusion, BP and HR are to be measured every 3 hours until 12 hours following end of infusion, then every 6 hours for 48 hours and then every 24 hours until the earlier of Day 5 or Discharge. All measurements should be performed as close as possible to specified timepoints. BP and HR are to be measured with the patient in the same position and with the same equipment using the same arm, throughout study drug infusion. These measurements may be made and recorded by trained healthcare personnel as part of their routine clinical duties, as well as trained study personnel. Refer to [Section 6.5.2](#).

j Blood will be locally collected and analyzed daily during hospitalization. If discharge occurs prior to Day 5, local blood collection will not be required at the Day 5 hospital/clinic visit. Following randomization, local laboratory collections can be adjusted to conform to the hospital's routine laboratory collection schedule and can be collected at any time of day. Refer to [Section 6.5.4](#).

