## 14 Appendix 1: Clinically notable laboratory values

Clinically notable laboratory abnormalities for selected tests based on a percent change from baseline (screening laboratory):

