Table 2-5 Primary, secondary and exploratory variables	15
Table 2-6 IV loop diuretics.....	23
Table 2-7 Safety risk and event of interest search specification	27
Table 2-8 Criteria for evaluating liver toxicity.....	31
Table 2-9 Nominal one-sided alpha at 70% randomized subjects accrued if CVD is rejected	34
Table 2-10 Assumed effect sizes for worsening heart failure and the key secondary efficacy variables on power calculation.....	36
Table 2-11 Powers (unconditional) of primary and key secondary variables on selected scenarios	36

Document History – Changes compared to previous version of RAP module 3.

Version	Date	Changes
Amendment 1	13-Aug-2015	
 -add the testing strategy for WHF and secondary endpoints in case of early stopping -add sensitivity analysis for WHF using logistic regression -add substudy population definition
Amendment 2	06-Feb-2017	
 - Clarify the method of mapping discharge visit to scheduled visits if scheduled visits are missing - Update the list of countries that recruited subjects (Table 2-3) - Remove subgroup category of lymphocytes and education level in Table 2-4 - Use FAS in section 2.1.9 – study medication summary. - Align presentation of non-IV concomitant medications with RELAX-AHF - Clarify definition of the censoring date for death endpoints (Adjudicated CV death, adjudicated all cause death) for patients who withdrew consent in countries where vital status data is publically available, in accordance with local laws and regulations - Clarify use of discharge date as the reference date for endpoint time to the composite endpoint of CV death or rehospitalization due to HF/RF during a follow-up period of 30 days post-discharge - Clarify the statistical method used for subgroup analysis of length of stay (LOS). Clarify the imputation rule for missing discharge information to align with RELAX-AHF - Clarify the imputation of signs and symptoms through Day 5 for subjects with WHF or died at hospital to align with RELAX-AHF - Addition of two new tables per ClinicalTrials.gov and EudraCT requirement -Update Safety risk and event of interest search specification (Table 2-7) - Clarify the ECG analysis population - Update the ECG categorical analysis, add analysis of newly occurring abnormalities in ECG morphology and remove ECG shift table to enable comprehensive assessment - Update liver function categorical analysis (Table 2-8)

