The CRLX030A2301 study (also referred to as RELAX-AHF-2) aims to evaluate the efficacy, safety and tolerability of intravenous infusion of 30 µg/kg/day serelaxin for 48 hours, when added to standard therapy. Data from this study is intended to replicate the reduction in mortality in AHF patients observed in the RELAX-AHF study.

The purpose of this document is to outline the planned analyses to be completed to support the completion of the Clinical Study Report (CSR) for RELAX AHF-2.

2 Statistical methods planned in the protocol and determination of sample size

Data will be analyzed according to the data analysis section 10 of the study protocol which is available in [Appendix 16.1.1 of the CSR](#).

All nominal time points will be used for analysis; actual assessment times will not be used to reclassify the time point at which a measure was taken. Time-to-event analyses will be based on actual dates (time) reported.

All references to index hospitalization refer to the initial hospitalization for AHF.

Unless specified, descriptive statistics indicates mean, median, standard deviation, minimum and maximum will be presented for continuous variables; the number and percentage of subjects in each category will be presented for categorical variables for each treatment group and all subjects (total).

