2.3.2 Laboratory data

2.3.2.1 Hematology and chemistry

In addition to local laboratory evaluations for all randomized subject, a laboratory substudy will be conducted at a subset of selected sites to enroll at least 1600 subjects. Subjects without written informed consent for the laboratory substudy before any study-specific assessment is performed will be excluded from the population.

Descriptive summaries of actual and change from baseline will be presented for all continuous clinical laboratory values by treatment and time point.

Clinical shift tables showing the pattern of change from baseline versus each post-baseline time point will be presented based on the cross-classification of the number of subjects with clinical laboratory values below (low), within (normal), or above (high) normal ranges for each laboratory test.

All laboratory data will be listed for each subject. Laboratory values that are outside the normal ranges will be flagged high (H) or low (L).

The number and percentage of subjects with clinically notable laboratory results, including categorical analysis on laboratory parameters of interest after baseline will be presented. Clinically notable laboratory values are defined in protocol Appendix 1. The notable laboratory values related to liver function are detailed in [Section 2.3.7](#).

The data from local and central laboratory will be presented separately.

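### SAP 2.3.2.1 specifies by-visit low/normal/high laboratory shift tables where protocol 10.5.2 plans baseline-to-most-extreme tables, so some tests have no per-patient worst-value summary

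*Protocol*

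**What the plan says.** Protocol section 10.5.2 (Safety variables): "Laboratory data will be summarized by presenting shift tables using extended normal ranges (baseline to most extreme post-baseline value". This gives each patient one entry per test, set by the most extreme value after baseline. The protocol does not define the extended ranges.

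SAP section 2.3.2.1 (Hematology and chemistry): "Clinical shift tables showing the pattern of change from baseline versus each post-baseline time point will be presented". The categories are "values below (low), within (normal), or above (high) normal ranges for each laboratory test". No table of baseline against the most extreme value appears in the SAP, and no extended ranges.

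SAP section 2 states: "Data will be analyzed according to the data analysis section 10 of the study protocol". It declares no departure for laboratory data.

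The SAP has other per-patient laboratory summaries. Section 2.3.2.1 adds: "The number and percentage of subjects with clinically notable laboratory results, including categorical analysis on laboratory parameters of interest after baseline will be presented". It refers to protocol Appendix 1 for the definition: "Clinically notable laboratory abnormalities for selected tests based on a percent change from baseline (screening laboratory". SAP section 2.3.2.2 counts creatinine and GFR changes at each and at any time point. SAP Table 2-8 counts graded multiples of the upper limit for liver tests. All values are listed, with high and low flags.

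**The concern.** The two plans differ in both dimensions of the table. The time axis goes from one worst value per patient to a separate table at each visit. The categories go from extended ranges to low, normal and high.

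The first change means that a short-lived abnormality appears in one visit's table and is absent from the others, so the number of patients who ever had it cannot be read off. The second means that a value already outside the normal range can move further out without changing cell. The drug is infused for 48 hours, so brief laboratory changes are among the things a safety display should show.

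A further feature affects the local data. Protocol Table 6-1, footnote j, says: "If discharge occurs prior to Day 5, local blood collection will not be required at the Day 5 hospital/clinic visit". Later by-visit local tables therefore cover mainly patients still in hospital. Shorter stay is a key secondary objective, so that group could differ between arms.

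**Working it through.** No sample size, power or alpha is involved. The check is a comparison of texts, a count of tests, and one threshold calculation.

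**1. The two tables**

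| Feature | Protocol 10.5.2 | SAP 2.3.2.1 |
|---|---|---|
| Time axis | Baseline to most extreme post-baseline value | Baseline to each post-baseline time point |
| Categories | Extended normal ranges (undefined) | Low, normal, high |
| Entries per patient and test | One per direction | One per visit sampled |

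Suppose n1, ..., nk patients shift from normal to low at visits 1 to k. The number who were ever low lies anywhere between the largest n and the smaller of the sum of the n's and the number of patients. The by-visit tables do not fix it.

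**2. Which tests keep another per-patient summary**

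Inputs: protocol 6.5.4.1 and 6.5.4.2 (local tests), 6.5.4.3 (central tests), Appendix 1, SAP 2.3.2.2 and SAP Table 2-8. The white-cell differential counts as one item. Tests done only at screening or baseline (BNP/NT-proBNP, hemoglobin A1c) are left out.

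- Local, with a criterion (10): hemoglobin, hematocrit, white cells, potassium, BUN or urea, creatinine, AST, ALT, alkaline phosphatase, total bilirubin.
- Local, without (3): sodium, glucose, differential. Total 10 + 3 = 13.
- Central, with a criterion (14): the same 10 plus red cells, platelets, calcium and uric acid.
- Central, without (12): sodium, glucose, differential, MCV, MCH, LDH, chloride, phosphorus, total protein, albumin, cholesterol, triglycerides. Total 14 + 12 = 26.

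For the tests without a criterion, the specified summaries are by-visit descriptive statistics, by-visit three-category shifts and listings. The minimum and maximum in the descriptive statistics describe an arm at a visit. They do not count patients.

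**3. Where a criterion exists but is coarse**

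Appendix 1 counts a fall in hemoglobin, hematocrit or potassium only if it exceeds 25%. With baseline b and lower normal limit L, a value is low but not notable if it lies from 0.75b up to just below L. Such values exist for every normal baseline below L/0.75 = 1.33L, whatever L is.

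Example with assumed values (the documents give no reference range): potassium falls from 4.2 to 3.2, with L = 3.5. The fall is (4.2 − 3.2)/4.2 = 23.8%. The patient crosses the limit but is not notable. With this L, the gap exists for baselines from 3.5 up to 3.5/0.75 = 4.67. One worst-value table would count the patient once.

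SAP Table 2-7 names transient hemoglobin/hematocrit decrease as a safety risk and hypokalemia as an event of interest, but searches for them through adverse event terms. Under protocol 7.1 an abnormal value is an adverse event only if it causes signs or symptoms, is judged clinically significant, or needs therapy.

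**4. Sampling**

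Under protocol 6.5.4, local samples are daily in hospital up to Day 5 and at discharge. Central substudy samples are also taken at Day 5 after earlier discharge, and at Day 14. The changing denominator is thus mainly a local-data problem.

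**The case against.** The strongest reply is that little is lost. Most tests have a percent-change or graded criterion that picks up a marked change whatever the baseline category. Every value is listed and flagged, and clinically significant abnormalities are recorded as adverse events. The SAP says it follows protocol section 10, so the protocol's table may still be intended. The undefined extended ranges leave open how much worsening it would have shown. SAP 2.3.2.1 also promises a categorical analysis of parameters of interest, which could include sodium or glucose.

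Much of this stands, and it limits the point to the tests and falls identified above. It does not remove it. The SAP names no parameter of interest. Listings for a trial of about 6,800 patients are not a summary. A general statement of conformity does not settle which of two different tables will be produced.

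A reader might go further in four ways that the documents do not support.

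- *All worst-value information is gone.* SAP 2.3.2.2, SAP Table 2-8 and the Appendix 1 counts contradict this.
- *Renal worsening is hidden because patients enter with impaired renal function.* Creatinine and GFR changes are counted at several thresholds at any time point, and BUN has an Appendix 1 row.
- *The silence of the SAP's change history shows an undeclared amendment.* That table does record "add analysis of newly occurring abnormalities in ECG morphology and remove ECG shift table", but it tracks changes between SAP versions, not differences from the protocol.
- *A loss of power can be stated.* Neither document plans a significance test on these tables or gives laboratory event rates, so any figure would be invented.

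It is also fair to say that restoring the protocol's table does not cure the discharge problem. For local data, a worst value through Day 5 depends on how many in-hospital samples a patient had.

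**Conclusion.** The point holds in a limited form. Protocol 10.5.2 and SAP 2.3.2.1 specify different laboratory shift tables and must be reconciled. In the SAP as written, 3 of 13 local and 12 of 26 central tests have no tabulated per-patient worst value and no tabulated worsening of an already abnormal value. In addition, falls of 25% or less in hemoglobin, hematocrit or potassium that briefly cross the normal limit are counted only visit by visit, although the SAP itself singles out these risks.

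This rests on two readings: that the SAP's table stands in place of the protocol's, and that the unnamed parameters of interest do not already cover the gap. The potassium example uses an assumed reference limit, but the algebra does not depend on it. This is a gap in descriptive safety reporting. It does not touch the primary or key secondary efficacy analyses.

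**What to change.** In SAP 2.3.2.1, before unblinding:

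1. Restore the protocol's shift table by arm: baseline category against the category of the most extreme post-baseline value, done once for the lowest and once for the highest value of each test.
2. Define the extended ranges for each test, so that movement within the abnormal zone is visible.
3. Present local and central data separately, as the SAP already does for other laboratory output.
4. Give the table through 48 hours, which covers the infusion and is least affected by discharge, and through Day 5. Footnote the local Day 5 table to say that the worst value depends on the number of in-hospital samples.
5. Keep the by-visit tables as supportive.

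If the sponsor prefers the by-visit tables alone, the SAP should state the departure from protocol 10.5.2 and give the reason.

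The cost is one extra set of standard tables from data already collected, plus the work of defining the ranges. No patient, visit or sample is added.
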